| Symptom | Severity | Group 1 2013 3.75+AS03/ 2017 3.75+AS03 (D1-D22) (N=X) | | Group 2 2013 3.75+AS03/ 2017 3.75+AS03 (D1-D121) (N=X) | | Group 3 2013 3.75+AS03/ 2017 15 (D1-D121) (N=X) | | Group 4 2017 3.75+AS03/ 2017 3.75+AS03 (D1-D22) (N=X) | | Group 5 2017 3.75+AS03/ 2017 3.75+AS03 (D1-D121) (N=X) | | Group 6 2017 3.75+AS03/ 2017 15 (D1-D121) (N=X) | | All Subjects (N=X) | |
|-----------------------------|----------|--|---------------|---|---------------|--|---------------|--|---------------|---|---------------|--|---------------|-----------------------|---------------|
| | | n | % (95% CI) | n | % (95% CI) | n | % (95% CI) | n | % (95% CI) | n | % (95% CI) | n | % (95% CI) | n | % (95% CI) |
| | Mild | x | xx (xx-xx) | x | xx (xx-xx) | x | xx (xx-xx) | x | xx (xx-xx) | x | xx (xx-xx) | x | xx (xx-xx) | x | xx (xx-xx) |
| | Moderate | x | xx (xx-xx) | x | xx (xx-xx) | x | xx (xx-xx) | x | xx (xx-xx) | x | xx (xx-xx) | x | xx (xx-xx) | x | xx (xx-xx) |
| | Severe | x | xx (xx-xx) | x | xx (xx-xx) | x | xx (xx-xx) | x | xx (xx-xx) | x | xx (xx-xx) | x | xx (xx-xx) | x | xx (xx-xx) |
| Ecchymosis | None | x | xx (xx-xx) | x | xx (xx-xx) | x | xx (xx-xx) | x | xx (xx-xx) | x | xx (xx-xx) | x | xx (xx-xx) | x | xx (xx-xx) |
| | Mild | x | xx (xx-xx) | x | xx (xx-xx) | x | xx (xx-xx) | x | xx (xx-xx) | x | xx (xx-xx) | x | xx (xx-xx) | x | xx (xx-xx) |
| | Moderate | x | xx (xx-xx) | x | xx (xx-xx) | x | xx (xx-xx) | x | xx (xx-xx) | x | xx (xx-xx) | x | xx (xx-xx) | x | xx (xx-xx) |
| | Severe | x | xx (xx-xx) | x | xx (xx-xx) | x | xx (xx-xx) | x | xx (xx-xx) | x | xx (xx-xx) | x | xx (xx-xx) | x | xx (xx-xx) |
| Ecchymosis (measurement) | None | x | xx (xx-xx) | x | xx (xx-xx) | x | xx (xx-xx) | x | xx (xx-xx) | x | xx (xx-xx) | x | xx (xx-xx) | x | xx (xx-xx) |
| | Mild | x | xx (xx-xx) | x | xx (xx-xx) | x | xx (xx-xx) | x | xx (xx-xx) | x | xx (xx-xx) | x | xx (xx-xx) | x | xx (xx-xx) |
| | Moderate | x | xx (xx-xx) | x | xx (xx-xx) | x | xx (xx-xx) | x | xx (xx-xx) | x | xx (xx-xx) | x | xx (xx-xx) | x | xx (xx-xx) |
| | Severe | x | xx (xx-xx) | x | xx (xx-xx) | x | xx (xx-xx) | x | xx (xx-xx) | x | xx (xx-xx) | x | xx (xx-xx) | x | xx (xx-xx) |
| Erythema | None | x | xx (xx-xx) | x | xx (xx-xx) | x | xx (xx-xx) | x | xx (xx-xx) | x | xx (xx-xx) | x | xx (xx-xx) | x | xx (xx-xx) |
| | Mild | x | xx (xx-xx) | x | xx (xx-xx) | x | xx (xx-xx) | x | xx (xx-xx) | x | xx (xx-xx) | x | xx (xx-xx) | x | xx (xx-xx) |
| | Moderate | x | xx (xx-xx) | x | xx (xx-xx) | x | xx (xx-xx) | x | xx (xx-xx) | x | xx (xx-xx) | x | xx (xx-xx) | x | xx (xx-xx) |
| | Severe | x | xx (xx-xx) | x | xx (xx-xx) | x | xx (xx-xx) | x | xx (xx-xx) | x | xx (xx-xx) | x | xx (xx-xx) | x | xx (xx-xx) |
| Erythema (measurement) | None | x | xx (xx-xx) | x | xx (xx-xx) | x | xx (xx-xx) | x | xx (xx-xx) | x | xx (xx-xx) | x | xx (xx-xx) | x | xx (xx-xx) |
| | Mild | x | xx (xx-xx) | x | xx (xx-xx) | x | xx (xx-xx) | x | xx (xx-xx) | x | xx (xx-xx) | x | xx (xx-xx) | x | xx (xx-xx) |
| | Moderate | x | xx (xx-xx) | x | xx (xx-xx) | x | xx (xx-xx) | x | xx (xx-xx) | x | xx (xx-xx) | x | xx (xx-xx) | x | xx (xx-xx) |

| Symptom | Severity | Group 1 2013 3.75+AS03/ 2017 3.75+AS03 (D1-D22) (N=X) | | Group 2 2013 3.75+AS03/ 2017 3.75+AS03 (D1-D121) (N=X) | | Group 3 2013 3.75+AS03/ 2017 15 (D1-D121) (N=X) | | Group 4 2017 3.75+AS03/ 2017 3.75+AS03 (D1-D22) (N=X) | | Group 5 2017 3.75+AS03/ 2017 3.75+AS03 (D1-D121) (N=X) | | Group 6 2017 3.75+AS03/ 2017 15 (D1-D121) (N=X) | | All Subjects (N=X) | |
|--------------------------------------|----------|--|---------------|---|---------------|--|---------------|--|---------------|---|---------------|--|---------------|-----------------------|---------------|
| | | n | % (95% CI) | n | % (95% CI) | n | % (95% CI) | n | % (95% CI) | n | % (95% CI) | n | % (95% CI) | n | % (95% CI) |
| | Severe | x | xx (xx-xx) | x | xx (xx-xx) | x | xx (xx-xx) | x | xx (xx-xx) | x | xx (xx-xx) | x | xx (xx-xx) | x | xx (xx-xx) |
| Induration/Swelling | None | x | xx (xx-xx) | x | xx (xx-xx) | x | xx (xx-xx) | x | xx (xx-xx) | x | xx (xx-xx) | x | xx (xx-xx) | x | xx (xx-xx) |
| | Mild | x | xx (xx-xx) | x | xx (xx-xx) | x | xx (xx-xx) | x | xx (xx-xx) | x | xx (xx-xx) | x | xx (xx-xx) | x | xx (xx-xx) |
| | Moderate | x | xx (xx-xx) | x | xx (xx-xx) | x | xx (xx-xx) | x | xx (xx-xx) | x | xx (xx-xx) | x | xx (xx-xx) | x | xx (xx-xx) |
| | Severe | x | xx (xx-xx) | x | xx (xx-xx) | x | xx (xx-xx) | x | xx (xx-xx) | x | xx (xx-xx) | x | xx (xx-xx) | x | xx (xx-xx) |
| Induration/Swelling (measurement) | None | x | xx (xx-xx) | x | xx (xx-xx) | x | xx (xx-xx) | x | xx (xx-xx) | x | xx (xx-xx) | x | xx (xx-xx) | x | xx (xx-xx) |
| | Mild | x | xx (xx-xx) | x | xx (xx-xx) | x | xx (xx-xx) | x | xx (xx-xx) | x | xx (xx-xx) | x | xx (xx-xx) | x | xx (xx-xx) |
| | Moderate | x | xx (xx-xx) | x | xx (xx-xx) | x | xx (xx-xx) | x | xx (xx-xx) | x | xx (xx-xx) | x | xx (xx-xx) | x | xx (xx-xx) |
| | Severe | x | xx (xx-xx) | x | xx (xx-xx) | x | xx (xx-xx) | x | xx (xx-xx) | x | xx (xx-xx) | x | xx (xx-xx) | x | xx (xx-xx) |

N = Number of subjects in the Safety Population who received any study vaccination; n = Number of subjects reporting event.

95% CI estimated using Clopper-Pearson exact method.

Severity is the maximum severity reported over all solicited symptoms post dosing for each subject.

Tables with similar format:

Table 90: Number and Percentage of Subjects Experiencing Solicited Events by Symptom, Maximum Severity and Study Group (Safety Population) – Post Study Vaccination 1

[Footnote Update] N = Number of subjects in the Safety Population who received the first study vaccination = Number of subjects reporting event.

Table 91: Number and Percentage of Subjects Experiencing Solicited Events by Symptom, Maximum Severity and Study Group (Safety Population) – Post Study Vaccination 2

[Footnote Update] N = Number of subjects in the Safety Population who received the second study vaccination; n = Number of subjects reporting event.

Table 92: Number and Percentage of Subjects Experiencing Solicited Events by Symptom, Severity, Day Post Study Vaccination, and Study Group (Safety Population) – Post Any Study Vaccination

| Symptom | Severity | Pre-Vac | | Post-Vac | | Day 1 | | Day 2 | | Day 3 | | Day 4 | | Day 5 | | Day 6 | | Day 7 | | Day 8+ | |
|---|----------|---------|----|----------|----|-------|----|-------|----|-------|----|-------|----|-------|----|-------|----|-------|----|--------|----|
| | | n | % | n | % | n | % | n | % | n | % | n | % | n | % | n | % | n | % | n | % |
| Group 1: 2013 3.75+AS03/ 2017 3.75+AS03 (D1-D22) (N=X) | | | | | | | | | | | | | | | | | | | | | |
| Any Symptom | None | x | xx | x | xx | x | xx | x | xx | x | xx | x | xx | x | xx | x | xx | x | xx | x | xx |
| | Mild | x | xx | x | xx | x | xx | x | xx | x | xx | x | xx | x | xx | x | xx | x | xx | x | xx |
| | Moderate | x | xx | x | xx | x | xx | x | xx | x | xx | x | xx | x | xx | x | xx | x | xx | x | xx |
| | Severe | x | xx | x | xx | x | xx | x | xx | x | xx | x | xx | x | xx | x | xx | x | xx | x | xx |
| Any Systemic Symptom | None | x | xx | x | xx | x | xx | x | xx | x | xx | x | xx | x | xx | x | xx | x | xx | x | xx |
| | Mild | x | xx | x | xx | x | xx | x | xx | x | xx | x | xx | x | xx | x | xx | x | xx | x | xx |
| | Moderate | x | xx | x | xx | x | xx | x | xx | x | xx | x | xx | x | xx | x | xx | x | xx | x | xx |
| | Severe | x | xx | x | xx | x | xx | x | xx | x | xx | x | xx | x | xx | x | xx | x | xx | x | xx |
| Fever | None | x | xx | x | xx | x | xx | x | xx | x | xx | x | xx | x | xx | x | xx | x | xx | x | xx |
| | Mild | x | xx | x | xx | x | xx | x | xx | x | xx | x | xx | x | xx | x | xx | x | xx | x | xx |
| | Moderate | x | xx | x | xx | x | xx | x | xx | x | xx | x | xx | x | xx | x | xx | x | xx | x | xx |
| | Severe | x | xx | x | xx | x | xx | x | xx | x | xx | x | xx | x | xx | x | xx | x | xx | x | xx |
| Feverishness | None | x | xx | x | xx | x | xx | x | xx | x | xx | x | xx | x | xx | x | xx | x | xx | x | xx |
| | Mild | x | xx | x | xx | x | xx | x | xx | x | xx | x | xx | x | xx | x | xx | x | xx | x | xx |
| | Moderate | x | xx | x | xx | x | xx | x | xx | x | xx | x | xx | x | xx | x | xx | x | xx | x | xx |
| | Severe | x | xx | x | xx | x | xx | x | xx | x | xx | x | xx | x | xx | x | xx | x | xx | x | xx |
| Fatigue | None | x | xx | x | xx | x | xx | x | xx | x | xx | x | xx | x | xx | x | xx | x | xx | x | xx |
| | Mild | x | xx | x | xx | x | xx | x | xx | x | xx | x | xx | x | xx | x | xx | x | xx | x | xx |
| | Moderate | x | xx | x | xx | x | xx | x | xx | x | xx | x | xx | x | xx | x | xx | x | xx | x | xx |
| | Severe | x | xx | x | xx | x | xx | x | xx | x | xx | x | xx | x | xx | x | xx | x | xx | x | xx |

| Symptom | Severity | Pre-Vac | | Post-Vac | | Day 1 | | Day 2 | | Day 3 | | Day 4 | | Day 5 | | Day 6 | | Day 7 | | Day 8+ | |
|-------------------|----------|---------|----|----------|----|-------|----|-------|----|-------|----|-------|----|-------|----|-------|----|-------|----|--------|----|
| | | n | % | n | % | n | % | n | % | n | % | n | % | n | % | n | % | n | % | n | % |
| Malaise | None | x | xx | x | xx | x | xx | x | xx | x | xx | x | xx | x | xx | x | xx | x | xx | x | xx |
| | Mild | x | xx | x | xx | x | xx | x | xx | x | xx | x | xx | x | xx | x | xx | x | xx | x | xx |
| | Moderate | x | xx | x | xx | x | xx | x | xx | x | xx | x | xx | x | xx | x | xx | x | xx | x | xx |
| | Severe | x | xx | x | xx | x | xx | x | xx | x | xx | x | xx | x | xx | x | xx | x | xx | x | xx |
| Myalgia | None | x | xx | x | xx | x | xx | x | xx | x | xx | x | xx | x | xx | x | xx | x | xx | x | xx |
| | Mild | x | xx | x | xx | x | xx | x | xx | x | xx | x | xx | x | xx | x | xx | x | xx | x | xx |
| | Moderate | x | xx | x | xx | x | xx | x | xx | x | xx | x | xx | x | xx | x | xx | x | xx | x | xx |
| | Severe | x | xx | x | xx | x | xx | x | xx | x | xx | x | xx | x | xx | x | xx | x | xx | x | xx |
| Arthralgia | None | x | xx | x | xx | x | xx | x | xx | x | xx | x | xx | x | xx | x | xx | x | xx | x | xx |
| | Mild | x | xx | x | xx | x | xx | x | xx | x | xx | x | xx | x | xx | x | xx | x | xx | x | xx |
| | Moderate | x | xx | x | xx | x | xx | x | xx | x | xx | x | xx | x | xx | x | xx | x | xx | x | xx |
| | Severe | x | xx | x | xx | x | xx | x | xx | x | xx | x | xx | x | xx | x | xx | x | xx | x | xx |
| Headache | None | x | xx | x | xx | x | xx | x | xx | x | xx | x | xx | x | xx | x | xx | x | xx | x | xx |
| | Mild | x | xx | x | xx | x | xx | x | xx | x | xx | x | xx | x | xx | x | xx | x | xx | x | xx |
| | Moderate | x | xx | x | xx | x | xx | x | xx | x | xx | x | xx | x | xx | x | xx | x | xx | x | xx |
| | Severe | x | xx | x | xx | x | xx | x | xx | x | xx | x | xx | x | xx | x | xx | x | xx | x | xx |
| Nausea | None | x | xx | x | xx | x | xx | x | xx | x | xx | x | xx | x | xx | x | xx | x | xx | x | xx |
| | Mild | x | xx | x | xx | x | xx | x | xx | x | xx | x | xx | x | xx | x | xx | x | xx | x | xx |
| | Moderate | x | xx | x | xx | x | xx | x | xx | x | xx | x | xx | x | xx | x | xx | x | xx | x | xx |
| | Severe | x | xx | x | xx | x | xx | x | xx | x | xx | x | xx | x | xx | x | xx | x | xx | x | xx |
| Any Local Symptom | None | x | xx | x | xx | x | xx | x | xx | x | xx | x | xx | x | xx | x | xx | x | xx | x | xx |
| | Mild | x | xx | x | xx | x | xx | x | xx | x | xx | x | xx | x | xx | x | xx | x | xx | x | xx |
| | Moderate | x | xx | x | xx | x | xx | x | xx | x | xx | x | xx | x | xx | x | xx | x | xx | x | xx |

| Symptom | Severity | Pre-Vac | | Post-Vac | | Day 1 | | Day 2 | | Day 3 | | Day 4 | | Day 5 | | Day 6 | | Day 7 | | Day 8+ | |
|--------------------------|----------|---------|----|----------|----|-------|----|-------|----|-------|----|-------|----|-------|----|-------|----|-------|----|--------|----|
| | | n | % | n | % | n | % | n | % | n | % | n | % | n | % | n | % | n | % | n | % |
| Pain | Severe | x | xx | x | xx | x | xx | x | xx | x | xx | x | xx | x | xx | x | xx | x | xx | x | xx |
| | None | x | xx | x | xx | x | xx | x | xx | x | xx | x | xx | x | xx | x | xx | x | xx | x | xx |
| | Mild | x | xx | x | xx | x | xx | x | xx | x | xx | x | xx | x | xx | x | xx | x | xx | x | xx |
| | Moderate | x | xx | x | xx | x | xx | x | xx | x | xx | x | xx | x | xx | x | xx | x | xx | x | xx |
| Tenderness | Severe | x | xx | x | xx | x | xx | x | xx | x | xx | x | xx | x | xx | x | xx | x | xx | x | xx |
| | None | x | xx | x | xx | x | xx | x | xx | x | xx | x | xx | x | xx | x | xx | x | xx | x | xx |
| | Mild | x | xx | x | xx | x | xx | x | xx | x | xx | x | xx | x | xx | x | xx | x | xx | x | xx |
| | Moderate | x | xx | x | xx | x | xx | x | xx | x | xx | x | xx | x | xx | x | xx | x | xx | x | xx |
| Pruritus | Severe | x | xx | x | xx | x | xx | x | xx | x | xx | x | xx | x | xx | x | xx | x | xx | x | xx |
| | None | x | xx | x | xx | x | xx | x | xx | x | xx | x | xx | x | xx | x | xx | x | xx | x | xx |
| | Mild | x | xx | x | xx | x | xx | x | xx | x | xx | x | xx | x | xx | x | xx | x | xx | x | xx |
| | Moderate | x | xx | x | xx | x | xx | x | xx | x | xx | x | xx | x | xx | x | xx | x | xx | x | xx |
| Ecchymosis | Severe | x | xx | x | xx | x | xx | x | xx | x | xx | x | xx | x | xx | x | xx | x | xx | x | xx |
| | None | x | xx | x | xx | x | xx | x | xx | x | xx | x | xx | x | xx | x | xx | x | xx | x | xx |
| | Mild | x | xx | x | xx | x | xx | x | xx | x | xx | x | xx | x | xx | x | xx | x | xx | x | xx |
| | Moderate | x | xx | x | xx | x | xx | x | xx | x | xx | x | xx | x | xx | x | xx | x | xx | x | xx |
| Ecchymosis (measurement) | Severe | x | xx | x | xx | x | xx | x | xx | x | xx | x | xx | x | xx | x | xx | x | xx | x | xx |
| | None | x | xx | x | xx | x | xx | x | xx | x | xx | x | xx | x | xx | x | xx | x | xx | x | xx |
| | Mild | x | xx | x | xx | x | xx | x | xx | x | xx | x | xx | x | xx | x | xx | x | xx | x | xx |
| | Moderate | x | xx | x | xx | x | xx | x | xx | x | xx | x | xx | x | xx | x | xx | x | xx | x | xx |
| Erythema | Severe | x | xx | x | xx | x | xx | x | xx | x | xx | x | xx | x | xx | x | xx | x | xx | x | xx |
| | None | x | xx | x | xx | x | xx | x | xx | x | xx | x | xx | x | xx | x | xx | x | xx | x | xx |
| | Mild | x | xx | x | xx | x | xx | x | xx | x | xx | x | xx | x | xx | x | xx | x | xx | x | xx |

| Symptom | Severity | Pre-Vac | | Post-Vac | | Day 1 | | Day 2 | | Day 3 | | Day 4 | | Day 5 | | Day 6 | | Day 7 | | Day 8+ | |
|--|----------|---------|----|----------|----|-------|----|-------|----|-------|----|-------|----|-------|----|-------|----|-------|----|--------|----|
| | | n | % | n | % | n | % | n | % | n | % | n | % | n | % | n | % | n | % | n | % |
| | Moderate | x | xx | x | xx | x | xx | x | xx | x | xx | x | xx | x | xx | x | xx | x | xx | x | xx |
| | Severe | x | xx | x | xx | x | xx | x | xx | x | xx | x | xx | x | xx | x | xx | x | xx | x | xx |
| Erythema (measurement) | None | x | xx | x | xx | x | xx | x | xx | x | xx | x | xx | x | xx | x | xx | x | xx | x | xx |
| | Mild | x | xx | x | xx | x | xx | x | xx | x | xx | x | xx | x | xx | x | xx | x | xx | x | xx |
| | Moderate | x | xx | x | xx | x | xx | x | xx | x | xx | x | xx | x | xx | x | xx | x | xx | x | xx |
| | Severe | x | xx | x | xx | x | xx | x | xx | x | xx | x | xx | x | xx | x | xx | x | xx | x | xx |
| Induration/Swelling | None | x | xx | x | xx | x | xx | x | xx | x | xx | x | xx | x | xx | x | xx | x | xx | x | xx |
| | Mild | x | xx | x | xx | x | xx | x | xx | x | xx | x | xx | x | xx | x | xx | x | xx | x | xx |
| | Moderate | x | xx | x | xx | x | xx | x | xx | x | xx | x | xx | x | xx | x | xx | x | xx | x | xx |
| | Severe | x | xx | x | xx | x | xx | x | xx | x | xx | x | xx | x | xx | x | xx | x | xx | x | xx |
| Induration/Swelling (measurement) | None | x | xx | x | xx | x | xx | x | xx | x | xx | x | xx | x | xx | x | xx | x | xx | x | xx |
| | Mild | x | xx | x | xx | x | xx | x | xx | x | xx | x | xx | x | xx | x | xx | x | xx | x | xx |
| | Moderate | x | xx | x | xx | x | xx | x | xx | x | xx | x | xx | x | xx | x | xx | x | xx | x | xx |
| | Severe | x | xx | x | xx | x | xx | x | xx | x | xx | x | xx | x | xx | x | xx | x | xx | x | xx |
| [repeat for all study groups & All Subjects] | | | | | | | | | | | | | | | | | | | | | |
| N = Number of subjects in the Safety Population who received any study vaccination; n = Number Severity is the maximum severity reported post dosing for each subject for each day. | | | | | | | | | | | | | | | | | | | | | |

[Implementation Note: The value considered for Day 8+ for each subject will be the maximum value reported at Day 8 or after for subjects with symptoms ongoing at Day 8.]

Tables with similar format:

Table 93: Number and Percentage of Subjects Experiencing Solicited Events by Symptom, Severity, Day Post Study Vaccination, and Study Group (Safety Population) – Post Study Vaccination 1

Table 94: Number and Percentage of Subjects Experiencing Solicited Events by Symptom, Severity, Day Post Study Vaccination, and Study Group (Safety Population) – Post Study Vaccination 2

Table 95: Number and Percentage of Subjects Experiencing Solicited Systemic Events for Study Vaccination 1 Compared with Study Vaccination 2 by Study Group– Safety Population

| | | Subjects with No Symptoms | Subjects with Mild or Greater Symptoms | Total Number of Subjects n (Percent) [p-value*] |
|---|--|---------------------------|--|---|
| Study Vaccination 1 vs Study Vaccination 2 | | | | |
| Group 1: 2013 3.75+AS03/ 2017 3.75+AS03 (D1-D22) (N=X) | Subjects with No Symptoms | x (%) | x (%) | x (%) |
| | Subjects with Mild or Greater Symptoms | x (%) | x (%) | x (%) |
| | Total Number of Subjects | x (%) | x (%) | x (100%) [0.xxx] |
| Group 2: 2013 3.75+AS03/ 2017 3.75+AS03 (D1-D121) (N=X) | Subjects with No Symptoms | x (%) | x (%) | x (%) |
| | Subjects with Mild or Greater Symptoms | x (%) | x (%) | x (%) |
| | Total Number of Subjects | x (%) | x (%) | x (100%) [0.xxx] |
| Group 3: 2013 3.75+AS03/ 2017 15 (D1-D121) (N=X) | Subjects with No Symptoms | x (%) | x (%) | x (%) |
| | Subjects with Mild or Greater Symptoms | x (%) | x (%) | x (%) |
| | Total Number of Subjects | x (%) | x (%) | x (100%) [0.xxx] |
| Group 4: 2017 3.75+AS03/ 2017 3.75+AS03 (D1-D22) (N=X) | Subjects with No Symptoms | x (%) | x (%) | x (%) |
| | Subjects with Mild or Greater Symptoms | x (%) | x (%) | x (%) |
| | Total Number of Subjects | x (%) | x (%) | x (100%) [0.xxx] |
| Group 5: | Subjects with No Symptoms | x (%) | x (%) | x (%) |
| | Subjects with Mild or Greater Symptoms | x (%) | x (%) | x (%) |

| | | Subjects with No Symptoms | Subjects with Mild or Greater Symptoms | Total Number of Subjects n (Percent) [p-value*] |
|--|--|---------------------------|--|---|
| 2017 3.75+AS03/ 2017 3.75+AS03 (D1-D121) (N=X) | Total Number of Subjects | x (%) | x (%) | x (100%) [0.xxx] |
| Group 6: 2017 3.75+AS03/ 2017 15 (D1-D121) (N=X) | Subjects with No Symptoms | x (%) | x (%) | x (%) |
| | Subjects with Mild or Greater Symptoms | x (%) | x (%) | x (%) |
| | Total Number of Subjects | x (%) | x (%) | x (100%) [0.xxx] |
| All Subjects (N=X) | Subjects with No Symptoms | x (%) | x (%) | x (%) |
| | Subjects with Mild or Greater Symptoms | x (%) | x (%) | x (%) |
| | Total Number of Subjects | x (%) | x (%) | x (100%) [0.xxx] |
| 
Note: Denominators for percentages are the number of subjects in the Safety Population who received both the first and second study vaccination. Subjects who did not receive both indicated vaccinations are not included in this table. [x] subjects did not receive the second study vaccination.
 
* P-value is calculated from McNemar's test for each study group.
 | | | | |

Table with similar format:

Table 96: Number and Percentage of Subjects Experiencing Solicited Local Events for Study Vaccination 1 Compared with Study Vaccination 2 by Study Group, Safety Population

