- Presence of signs or symptoms that could confound or confuse assessment of study vaccine reactogenicity. For subjects with injection site or systemic signs or symptoms, or with an acute illness, including an oral temperature greater than or equal to 100°F, the second study vaccination should be postponed/deferred until signs, symptoms or acute illness have/has resolved, or are/is improving as further specified below, and if within the acceptable protocol-specified window for the Dose 2 visit. No exceptions to the protocol-specified window will be made. **Note for afebrile, acute illness only:** If a subject is afebrile, his/her acute illness is nearly resolved with only minor residual symptoms remaining, this occurs within the acceptable protocol-specified window for the Dose 2 visit, and, in the opinion of the site PI or appropriate sub-investigator, the residual symptoms will not interfere with the ability to assess safety parameters as required by the protocol, the subject may receive the second study vaccination without further approval from the DMID Medical Officer. No exceptions to the protocol-specified window will be made.

- Grade 3 solicited or unsolicited AE that occurs without alternative etiology in the 8 days after the first study vaccination.
- Grade 3 solicited or unsolicited AE that is ongoing, whether or not it is improved or resolving.
- Any unresolved or ongoing Grade 2 solicited or unsolicited AE that does not decrease to Grade 1 or less prior to the second study vaccination. Note: An unresolved or ongoing Grade 1 solicited or unsolicited AE is permissible following the documented determination by the site PI or appropriate sub-investigator, that it would not render study vaccination unsafe or interfere with the evaluation of responses.
- Grade 3 clinical safety laboratory value (according to the toxicity table, [Section 9.2.3](#)) that does not decrease to Grade 2 or less prior to the second study vaccination. Note: Any clinical safety laboratory parameter may be re-evaluated only once at the central (clinical) laboratory in order to assess eligibility prior to the second study vaccination. If the clinical safety laboratory value decreases to Grade 2 or less, the subject may receive the second study vaccination. The second study vaccination should be scheduled to occur within the acceptable protocol-specified window for the Dose 2 visit. No exceptions to the protocol-specified window will be made.

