11.2 Study Hypotheses

This Phase II study is not designed to test a formal null hypothesis. Rather, it is intended to obtain sufficient data to obtain meaningful estimates of the immune response induced by this vaccine and to uncover any safety issues that occur at a sufficiently high rate that they might be observed in a study of this size. The sample size facilitates formal testing of selected hypotheses as discussed in [Section 11.4.3](#), along with the probability of observing safety outcomes and the precision of immunogenicity outcomes.

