$$\text{logit}[P(\text{Event})] = \beta_0 + \beta_1 \times \text{PrimeBoost} + \beta_2 \times \text{BoostDose} + \beta_3 \times \text{Interval} + \beta_4 \times (\text{PrimeBoost} * \text{BoostDose}) + \beta_5 \times (\text{PrimeBoost} * \text{Interval}) + \varepsilon,$$

For each systemic and local event, any systemic event, any local event, and any solicited event, the maximum severity over 7 days after each vaccination will be summarized for the Safety population. The number and percentage of subjects reporting each event will be summarized by the maximum severity and study group, separately for each vaccination and over both vaccinations. For each event the denominator is the number of subjects who received the applicable vaccination with non-missing data for the specific event. The 95% CI calculated using Clopper-Pearson methodology from a binomial distribution (SAS Proc Freq with a binomial option) will be presented ([Table 89](#), [Table 90](#), [Table 91](#)).

The number of subjects reporting a solicited adverse event will be summarized for each day post vaccination for each vaccination and for both vaccinations combined both in a summary table ([Table 92](#), [Table 93](#), [Table 94](#)) and graphically in a bar chart ([Figure 26](#) and [Figure 27](#)). A comparison of the event rate for each study group between study vaccinations will be presented, including p-values from McNemar's test performed ([Table 95](#), [Table 96](#)).

Systemic and Local solicited events reported by subject will be presented in [Listing 11](#) and [Listing 12](#), sorted by subject ID, vaccination number, parameter, and study day.

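### SAP Tables 95–96 test dose 1 against dose 2 without a paired difference and interval, and severe rates in Tables 90 and 91 are not like-for-like because dose 2 depends on the dose-1 reaction

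*SAP*

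**What the plan says.** **The comparison.** SAP 9.3.1 announces it as follows: "A comparison of the event rate for each study group between study vaccinations will be presented, including p-values from McNemar's test performed". The shells for Table 95 (systemic) and Table 96 (local) cross-classify subjects as having no symptoms or mild-or-greater symptoms after each dose. They print counts, percentages and both margins, per group and for all subjects. The footnotes add: "P-value is calculated from McNemar's test for each study group". Protocol 11.6.2 also names McNemar's test.

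**Who is in it.** "Denominators for percentages are the number of subjects in the Safety Population who received both the first and second study vaccination". The footnote continues: "Subjects who did not receive both indicated vaccinations are not included in this table". A further footnote gives the number who did not receive dose 2, without reason or dose-1 severity.

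**Who gets dose 2.** Among the criteria in Protocol 5.2.3 for not giving the second vaccination is: "Grade 3 solicited or unsolicited AE that occurs without alternative etiology in the 8 days after the first study vaccination". Some unresolved Grade 2 events also prevent it.

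**The severity tables.** Table 90 (after dose 1) counts everyone who received dose 1. Table 91 (after dose 2) has the footnote "N = Number of subjects in the Safety Population who received the second study vaccination; n = Number of subjects reporting event".

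**The purpose of the study.** Protocol 11.2: "This Phase II study is not designed to test a formal null hypothesis". That section and SAP section 5 state that meaningful estimates are the aim.

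**The concern.** There are two linked problems.

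1. The plan's only within-subject reactogenicity display attaches inference to the dose-to-dose change through a p-value and nothing else. With so few pairs, a non-significant result is compatible both with no change and with a large one. The p-value does not tell the reader which. An interval would.

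2. Whether a subject receives dose 2 depends partly on how that subject reacted to dose 1. A severe rate from Table 91 therefore comes from people who have passed that filter, while the Table 90 rate comes from everyone. Readers will set the two tables side by side, because together they answer the primary safety objective for each vaccination. Read that way, dose 2 looks somewhat better tolerated than it would in the same full set of subjects.

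**Working it through.** **Step 1. The plan's nearest figure.** No precision is stated for the paired comparison. SAP Table 7 gives 31–69% as the worst-case exact interval for one group of 30. Clopper-Pearson at 15/30 gives 31.3–68.7%, so the figure reproduces.

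**Step 2. What the p-value leaves out.** Let b be the subjects with symptoms after dose 1 only, c those after dose 2 only, and n the pairs. The exact McNemar p uses b and c alone. The change is (c − b)/n. For its interval I used Bonett-Price: p₂ = (c+1)/(n+2), p₁ = (b+1)/(n+2), d = p₂ − p₁, SE = √[(p₁ + p₂ − d²)/(n+2)], limits d ± 1.96·SE. All counts are assumed.

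| n | b | c | Change (points) | 95% interval | Exact p |
|---|---|---|---|---|---|
| 27 | 8 | 2 | −22.2 | −42.9 to 1.5 | 0.109 |
| 28 | 6 | 3 | −10.7 | −31.4 to 11.4 | 0.508 |
| 28 | 3 | 3 | 0.0 | −18.5 to 18.5 | 1 |
| 27 | 1 | 1 | 0.0 | −13.5 to 13.5 | 1 |

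First row: p₂ = 3/29 = 0.1034, p₁ = 9/29 = 0.3103, d = −0.2069, SE = √(0.3710/29) = 0.1131. The p-value is 2 × 56/1024 = 0.109. The last two rows share a p-value but differ in precision.

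**Step 3. Expected precision.** Protocol 11.4.2 expects per protocol exclusions of about 10% (4-month groups) and 5% (21-day groups), which include subjects without dose 2. I took 27 to 30 pairs on that basis. The half-width is about 1.96·√(s/n), where s is the discordant share (assumed 0.2–0.4).
- n = 30: 16.0 to 22.6 points.
- n = 27: 16.9 to 23.9 points.
- All groups together, n = 162 to 180: 6.5 to 9.7 points.

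**Step 4. How many lose dose 2.** If a share g of subjects has a qualifying Grade 3 event (assumed), the expected number in 30 is 30g, and the chance of at least one is 1 − (1−g)³⁰.
- g = 2%: 0.6 expected, 45% chance.
- g = 5%: 1.5 expected, 79% chance.
- g = 10%: 3.0 expected, 96% chance.

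**Step 5. Effect on the severe rate.** Assume equal true reactogenicity of both doses, bivariate normal latent severity with correlation ρ, and dose 2 withheld after every Grade 3 dose-1 reaction. If g₁₁ is the probability of Grade 3 after both doses, the rate seen among dose-2 recipients is (g − g₁₁)/(1 − g).

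| True g | ρ | g₁₁ | Rate seen after dose 2 |
|---|---|---|---|
| 5% | 0.3 | 0.71% | 4.29/95 = 4.5% |
| 5% | 0.7 | 1.96% | 3.04/95 = 3.2% |
| 10% | 0.3 | 2.16% | 7.84/90 = 8.7% |
| 10% | 0.7 | 4.68% | 5.32/90 = 5.9% |

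In a group of 30 this is a shortfall of about 0.15 to 1.2 subjects.

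**Step 6. Effect on Tables 95–96.** With a the rate of any reaction (assumed 60–70%), the dose-1 rate among two-dose subjects is (a − g)/(1 − g). At a = 60% and g = 10% this is 50/90 = 55.6%. The dose-2 rate in the same subjects is 57.9% at ρ = 0.3, a shift of 2.3 points, the largest in the range. The smallest is 0.02 points (a = 70%, g = 5%, ρ = 0.7). The direction is opposite to Step 5: here dose 2 looks slightly more reactogenic.

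**The case against.** **The tables do more than test.** A reader might infer that the doses are compared by a p-value alone and no change is estimated. The shell does not support that. It prints both margins, so the point change can be read off. Only its stated value and interval are missing.

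**The two-dose restriction is no fault.** McNemar's test needs pairs, the protocol specifies it, and the footnotes disclose both the restriction and the number without dose 2. This stands. Table 91's denominator is also the natural one for a post-dose-2 table, and it is labelled.

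**The selection hardly touches Tables 95–96.** Their outcome is none versus mild-or-greater, so a Grade 3 and a Grade 1 reactor fall in the same cell. Nor are all the worst reactors removed, because Grade 3 events with an alternative etiology fall outside the quoted criterion. Both points stand.

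**Much can be recovered elsewhere.** Table 16 gives dose-2 receipt by group, Listing 2 gives reasons for discontinuation, Listings 11–12 give severity by subject and dose, and Tables 85–86 and 90–91 give Clopper-Pearson intervals for each dose. That is true, but intervals for two separate rates do not give one for a paired difference, and a reader should not have to rebuild the matched severity display from listings.

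**Low power is no defect in a study not built to test hypotheses.** Agreed. That is a reason to report an estimate with its interval.

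**Missing diaries.** One might infer that a dose-2 recipient without diary data is counted as symptom-free. No text says so. SAP 9.3.1 bases percentages on non-missing data, SAP 6.5 rules out imputation, and every vaccinated subject has an in-clinic assessment. What remains is a wording mismatch: the Table 95 footnote defines its denominator by receipt of both doses.

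**Conclusion.** The point holds as a modest reporting gap. Tables 95–96 should carry the paired difference with its interval. With 27 to 30 pairs and discordance of 20–40%, that interval would reach about 16 to 24 points either side, and the p-value does not convey this.

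The documents do not support the stronger inference that the paired comparison is materially biased by removal of severe reactors; the shift is about 0 to 2 points. The selection matters when Table 91 is read against Table 90: an assumed 5% Grade 3 rate would show as 3.2–4.5%, and 10% as 5.9–8.7%.

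These sizes rest on assumed reaction rates, correlations of 0.3–0.7 and equal reactogenicity of the doses; the documents give none of them. Equality is least plausible in Groups 3 and 6, where dose 2 has no AS03, so there the figures isolate the selection effect and do not predict the observed contrast. The model treats every Grade 3 dose-1 reaction as disqualifying and ignores the unresolved Grade 2 criteria.

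**What to change.** - In Tables 95–96, add the paired difference (dose 2 minus dose 1) with a 95% interval, per group and overall. Name the interval method and keep the p-value.
- Reword the footnote so that the denominator is subjects with non-missing solicited data after both doses, in line with SAP 9.3.1.
- Replace the single count of subjects without dose 2 by a count per group, stating how many were not given it because of a dose-1 reaction.
- Beside Table 91, show the dose-1 severity of the same two-dose subjects, and note that the comparison applies to them.

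I would not add a row that imputes reactions to a dose that was never given: it answers a question the plan does not ask and conflicts with the no-imputation rule. The withholding rule in Protocol 5.2.3 is taken as it stands.

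The cost is SAP wording and slightly longer tables. No new data are needed.
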